### **10.1 Follow-up**

Adverse events not related to the study drug or study procedures will be followed up until final visit (V4). SAEs and adverse events for which relationship to the study drug or to the study procedures cannot be excluded will be followed up until resolution or stabilization, or until the Investigator judges safe to discontinue follow-up (to be justified in the CRF).

Planned medical procedures (not only surgical) which are not taken as an action to an event having occurred during the study, will not be followed-up and should not be considered as SAE, if already planned before the inclusion.

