#### *UNLIKELY*

There is another reasonable explanation for the event occurrence.

This means: A clinical event, including laboratory test abnormality, with a temporal relationship to drug intake that makes a causal relationship improbable, and in which other drugs, chemicals or underlying disease provide plausible explanations.

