#### *NOT ASSESSABLE*

There is insufficient or incomplete evidence to make a clinical judgement of the causal relationship.

This means: A report of an adverse reaction which cannot be judged because information is insufficient or contradictory, and which cannot be supplemented or verified.

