#### *NOT RELATED*

There is no evidence of any causal relationship.

This means: When sufficient information exists to indicate that the etiology is unrelated to the study drug.

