## **5 DEFINITIONS AND DATA CONVENTIONS**

### Age

Age will be calculated in decimal form as portion of the date of screening visit minus the date of birth, divided by 365.25 days per year, and then rounded down, that is:

$$\text{Age (years)} = \text{Floor}((\text{date of screening visit} - \text{date of birth}) / 365.25).$$

Body Mass Index (BMI)

BMI will be computed using the following formula:

$$\text{BMI} = \text{Body Weight (kg)} / (\text{Height (m)})^2$$

Daily dosage

Daily dosage (mcg) will be computed for each patient as:

$$\text{Daily Dosage} = \left( \frac{\sum_{i=1}^7 (\text{daily dosage}_i [\text{mcg}])}{7} \right)$$

where “i” is the day of the week.

Daily dosage/Body Weight

Daily dosage/Body Weight (mcg / kg) will be computed for each patient as:

$$\text{Daily Dosage/Body Weight} = \frac{\left( \frac{\sum_{i=1}^7 (\text{daily dosage}_i [\text{mcg}])}{7} \right)}{\text{Weight [kg]}}$$

where “i” is the day of the week.

Prior medications

Medications reported with an end date before the first study treatment administration (end date < date of first study treatment administration). As prior medication will be also indicated all medications reported by patients who didn't took the study treatment.

Concomitant medications

Medications reported as ongoing or with an end date after the first study treatment administration (ongoing or end date ≥ date of first study treatment administration).

Treatment-Emergent Adverse Events (TEAEs)

Adverse events who started after the start of the study treatment, adverse events without start date and with an end date after the start of the study treatment or adverse events without start date reported as ongoing (for patients who take at least one dose of study treatment).

Pre-Treatment Adverse Events (PTAEs)

Adverse events started after the subject's inclusion into the study but before the effective study treatment period (start date < date of first study treatment administration).

Serious Adverse Events (SAEs)

Adverse Event judged as serious.

Drug related Adverse Events

Adverse Events with a relationship to treatment reported as "Certain", "Probable" or "Possible".

Adverse events leading to discontinuation

Adverse Events leading to discontinuation is an AE with action taken equal to "Drug withdrawn".

Adverse events leading to death

Adverse Events leading to death is an AE with outcome equal to "Fatal".

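### The SAP's drug-related definition leaves out AEs rated Not assessable, so the drug-related AE and TEAE rates may be lower than under a conservative convention

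*SAP*

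**What the plan says.** SAP section 5 (Definitions and data conventions) defines drug-related adverse events as "Adverse Events with a relationship to treatment reported as" Certain, Probable or Possible. SAP 9.5.2 uses this definition for two tables by SOC and PT: drug-related AEs and drug-related TEAEs.

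The causality scale in protocol Appendix I has six grades. The three outside the SAP definition are described differently:

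- Unlikely: another reasonable explanation exists, and the event is one "with a temporal relationship to drug intake that makes a causal relationship improbable".
- Not assessable: "A report of an adverse reaction which cannot be judged because information is insufficient or contradictory, and which cannot be supplemented or verified".
- Not related: "When sufficient information exists to indicate that the etiology is unrelated to the study drug".

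Protocol 10.1 sets how long events are followed. Events not related to drug or procedures are followed to the final visit. By contrast, "SAEs and adverse events for which relationship to the study drug or to the study procedures cannot be excluded will be followed up until resolution". The same sentence also lets follow-up end once an event is stable or when the Investigator considers it safe to stop.

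The statistical section of the protocol (11.3.6, Safety Analyses) asks for numbers of patients with AEs and does not define drug related. The SAP's list of changes from the protocol (section 4) does not mention causality grouping. SAP section 8, on missing and incomplete data, covers partial AE dates but not unassessable or blank causality.

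**The concern.** Unlikely and Not related are both judgements against a causal link, and each needs some positive basis. Not assessable records that no judgement could be made. Under the SAP definition all three have the same result: the event does not appear in the drug-related tables. A reader of those tables could then take absent information for an absent relationship.

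The SAP is more cautious with another kind of missing AE information. In the same section 5, an event without a start date counts as treatment-emergent if it ended after treatment began or is ongoing, in patients who took at least one dose. No similar default is given for causality.

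What is at stake is how a descriptive figure is read. The study is open-label with a single arm, so there is no control rate against which to set the drug-related rate, and the definition therefore carries more weight. No endpoint, test or decision rule depends on it.

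**Working it through.** **Step 1. Set the grades side by side.**

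| Grade (protocol Appendix I) | Basis in the protocol | In SAP drug-related tables? | Protocol 10.1 group, if non-serious |
|---|---|---|---|
| Certain, Probable, Possible | Some or clear evidence for a link | Yes | Cannot be excluded |
| Unlikely | Another explanation; link improbable | No | Not stated; arguable either way |
| Not assessable | Cannot be judged | No | Cannot be excluded (inferred) |
| Not related | Sufficient information against a link | No | Not related |

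The Not assessable entry in the last column is an inference, because 10.1 does not name the grade. It follows from the definitions: Not related requires sufficient information, Not assessable means that information is lacking or contradictory, and an event that cannot be judged has not had its relationship excluded.

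**Step 2. Look for a plan figure to reproduce.** Neither document states a drug-related AE rate or the number of events rated Not assessable, so there is none.

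**Step 3. Direction.** Adding a category to the definition can only raise the patient-level rate or leave it unchanged.

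**Step 4. Size.** Inputs:

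- Denominator: the safety population is all included patients (SAP 6.3), and 47 were included in the treatment phase (SAP 4.1).
- k: the number of patients whose only candidate drug-related event is rated Not assessable. The documents do not give it, so a range of 0 to 5 is assumed.

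Shift in the drug-related rate = k / 47.

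| k (assumed) | Shift, percentage points |
|---|---|
| 0 | 0.0 |
| 1 | 1/47 = 2.1 |
| 2 | 2/47 = 4.3 |
| 3 | 3/47 = 6.4 |
| 5 | 5/47 = 10.6 |

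**Step 5. Compare with sampling uncertainty.** Suppose 2 patients have an event that counts as drug related under the current definition (an assumption, for illustration only). The rate is 2/47 = 4.3%, with an exact 95% interval of 0.5% to 14.5%. With k = 1 it becomes 3/47 = 6.4%, with an interval of 1.3% to 17.5%. A shift of one patient is small beside the uncertainty of any rate estimated in 47 patients.

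**The case against.** The strongest case on the other side has five parts.

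- **Protocol 10.1 is about follow-up.** It does not define drug related for analysis. It also places all SAEs in the longer follow-up group whatever their causality, so membership of that group shows caution and not relatedness. This stands. A reader might infer that the SAP contradicts a protocol analysis rule, but the protocol's safety analysis contains no such rule. The SAP's convention is simply not aligned with the protocol's caution.
- **Understatement is not shown.** A reader might infer that the drug-related rate is biased in favour of the product. The documents do not support this. The number of Not assessable events is unknown and may be zero, and an event that cannot be judged may in truth be unrelated, so counting it could overstate the rate. This also stands.
- **The same reasoning could reach Unlikely.** An improbable link is not an excluded one. This stands in part, and any fix must say where the line is drawn. There is a defensible line: Unlikely rests on a plausible alternative explanation, whereas Not assessable rests on no judgement.
- **No event is lost.** SAP 9.5.2 tabulates all AEs, all TEAEs and their serious subsets regardless of causality, and lists serious and fatal events. This stands and is the main reason for the low severity.
- **Missing ratings are not expected.** Protocol Appendix I says the physician will always be asked about causality, and protocol 11.1.2 provides electronic completeness checks. This is fair. A rule for blanks is only a safeguard, but it fits in the same sentence.

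**Conclusion.** The point holds in a limited form. The SAP states a rule that drops events with undetermined causality from the drug-related AE and TEAE tables, and it neither gives a reason nor reports how many are dropped. The drug-related rate may therefore be lower than under a conservative convention, by 2.1 percentage points for each affected patient out of 47. The actual size cannot be known from the documents and may be zero. The result rests on two things: that the safety population is the 47 included patients, and that an event which cannot be judged is one whose relationship has not been excluded. Overall AE counts, efficacy results and the study's conclusions on TSH are unaffected. Severity is low: worth changing because it is cheap, not because harm has been shown.

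**What to change.** In SAP section 5, extend the drug-related definition to Certain, Probable, Possible, Not assessable and any missing causality, and apply it to the drug-related AE and TEAE tables in SAP 9.5.2. Add a footnote or separate row giving the number of patients and events in the last two groups, so that the rate under the current definition can still be read. State that Unlikely remains outside because it rests on a stated alternative explanation. Record the choice as a reporting convention, and note that protocol 10.1 governs follow-up and not analysis.

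The cost is about one sentence of SAP text and one table footnote. No new data are needed, since Not assessable is already a grade on the protocol's causality scale. The downside is that the drug-related rate may be slightly less favourable and may include events that are not truly related. The separate count lets a reader see how much of the rate comes from them.

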## **6 ANALYSIS SETS**

### **6.1 INTENTION-TO-TREAT POPULATION (ITT)/ FULL ANALYSIS SET (FAS)**

All included patients who received at least one dose of the study medication.

### **6.2 PER-PROTOCOL POPULATION (PP)**

All patients in the ITT population who completed the study and who did not have any major protocol violations (e.g. use of prohibited concomitant medications, violation of major inclusion/exclusion criteria).

### **6.3 SAFETY POPULATION (SP)**

All included patients.

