### *11.3.2 Population for analysis*

The following populations will be considered for the analysis:

**Intent-To-Treat (ITT) population:** all included patients who received at least one dose of the study medication.

**Per-Protocol (PP) population:** all patients in the ITT population who completed the study and who did not have any major protocol violations (e.g. use of prohibited concomitant medications, violation of major inclusion/exclusion criteria).

**Safety Population:** all included patients.

All efficacy variables will be analyzed in both the ITTs and PP populations.

The safety analyses will be carried out in the safety population.

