## **4.1 SAMPLE SIZE**

A sample size of 48 subjects had 70% power to detect a difference in means of TSH of 0.7, assuming a standard deviation of differences of 1.9, using a paired t-test with a 0.050 two-sided significance level. To account for a drop-out and dose adjustment rate of about 20%, a maximum number of 60 subjects were to be included in the study (Tirosint® treatment phase).

The study was early terminated with 47 patients included in the Tirosint ® treatment phase and 45 patients completed, due to the COVID-19 pandemic outbreak.

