## 9.5 ANALYSIS OF SAFETY

The safety analyses will be carried out in the safety population.

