### 9.5.2 Adverse Events

Adverse events (AEs) intensity and frequency will be analysed during the pre-treatment phase and in the treatment phase until End of Study Visit.

The following summary tables will be provided:

- Adverse Events by SOC and PT;
- Serious Adverse Events by SOC and PT;

- Drug related Adverse Events by SOC and PT;
- Pre-Treatment Adverse Events by SOC and PT;
- Serious Pre-Treatment Adverse Events by SOC and PT;
- Treatment-Emergent Adverse Events by SOC and PT;
- Serious Treatment-Emergent Adverse Events by SOC and PT;
- Drug related Treatment-Emergent Adverse Events by SOC and PT;

Serious adverse events and fatal adverse events will also be listed.

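### The Safety Population has no dosing condition, so any included but never-dosed patient would lower the treatment-emergent AE percentages; the possible effect is small and may be nil

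*SAP*

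**What the plan says.** SAP 6.3 gives the Safety Population in three words: "All included patients". Protocol 11.3.2 uses the same definition ("all included patients"), so the SAP has carried the protocol over faithfully. SAP 6.1 defines the ITT/FAS set more narrowly: "All included patients who received at least one dose of the study medication".

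SAP 9.5 assigns the set: "The safety analyses will be carried out in the safety population". The tables in SAP 9.5.2 include "Treatment-Emergent Adverse Events by SOC and PT", with serious and drug-related versions. That section states no percentage denominator, and Appendix 2 contains no table shells.

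SAP 5 ties a TEAE to exposure. It covers "Adverse events who started after the start of the study treatment", and its rule for events without a start date is limited by the words "for patients who take at least one dose of study treatment".

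On numbers, SAP 4.1 reports: "The study was early terminated with 47 patients included in the Tirosint" treatment phase, of whom 45 completed. It does not say whether either of the other two took a capsule.

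**The concern.** The usual order of the sets is reversed: the efficacy set requires exposure, and the set used to describe the risk of exposure does not. For a TEAE percentage, the numerator is restricted to dosed patients by definition and the denominator is not. Any mismatch can act in one direction only, towards a lower rate, which favours the product.

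The situation is foreseeable. Under protocol 7.3, inclusion and dispensing happen at Visit 2, and the first capsule is to be taken that day only where feasible. Under protocol 9.1, the Visit 2 blood goes to a central laboratory and the result follows later. Protocol 5.4 lists a need for dose adjustment on receipt of that result as a reason for withdrawal. A patient could therefore be included and leave before the first capsule. The SAP's prior-medication rule (section 5) also provides for patients who took no study treatment, and SAP 7.3 summarises medications on the Safety Population.

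What is at stake is the accuracy of the descriptive on-capsule AE rates. No hypothesis test depends on it.

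**Working it through.** The plan states no TEAE rate and no count of undosed patients, so there is no figure on this point to reproduce. The one calculation beside the patient counts in SAP 4.1 does reproduce. With n = 48, a difference of 0.7 and an SD of differences of 1.9, the noncentrality is 0.7 / (1.9/√48) = 2.55 on 47 degrees of freedom. The two-sided 0.05 paired t-test then has 70.5% power, against the stated 70%. Likewise 48 / (1 − 0.20) = 60. Neither figure bears on the safety denominator.

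**Inputs**

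- Included in the treatment phase: 47 (SAP 4.1).
- Completed: 45 (SAP 4.1).
- Non-completers: 47 − 45 = 2.
- Run-in withdrawals are screening failures (protocol 5.4), so they are not in the Safety Population and do not add to the count.
- Number included but never dosed, u: not given. Assuming that every completer took at least one dose, u is 0, 1 or 2.
- Number of patients with a TEAE, x: not given. The values 14 and 20 below are assumptions for illustration.

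**Formulas**

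- Rate on all included patients: x / 47.
- Rate on dosed patients: x / (47 − u).
- Ratio of the first to the second: (47 − u) / 47.
- Relative understatement: u / 47, whatever the value of x.

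**Results**

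| u | Dosed | Ratio | Relative understatement | x = 14: all included vs dosed | x = 20: all included vs dosed |
|---|---|---|---|---|---|
| 0 | 47 | 1.000 | 0% | 29.8% vs 29.8% | 42.6% vs 42.6% |
| 1 | 46 | 0.979 | 2.1% | 29.8% vs 30.4% | 42.6% vs 43.5% |
| 2 | 45 | 0.957 | 4.3% | 29.8% vs 31.1% | 42.6% vs 44.4% |

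In absolute terms the largest gap is 1.3 points at x = 14 and 1.9 points at x = 20. The arithmetic ceiling is reached when u = 2 and all 45 dosed patients have a TEAE: 45/47 = 95.7% against 45/45 = 100%, a gap of 4.3 points.

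**The case against.** The strongest reply is that the gap may be empty. Capsules are handed out at the visit where inclusion occurs, intake is meant to start the same day, and SAP 4.1 counts the 47 as included in the treatment phase. The 4.3% figure needs both non-completers to have taken nothing, and no text supports that. The all-included denominator is also inferred from SAP 9.5, because 9.5.2 states none. The trial has a single arm and AE reporting is descriptive, so no comparison between arms is distorted. All of this stands, and it is why the point is conditional and minor.

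An all-included set also has a legitimate use. SAP 5 and 9.5.2 require tables of pre-treatment events, defined as those between inclusion and first dose, and this set takes in everyone who could have one. Redefining the whole Safety Population as dosed patients would make it identical to ITT and move never-dosed patients out of those tables. This stands too, and it shapes the fix.

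Three stronger readings are tempting but not supported:

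- A reader might infer that the AE rates are in fact biased low. No text reports an undosed included patient.
- A reader might take the prior-medication rule as naming included patients who went untreated. It speaks of patients without study treatment and does not say they were included. Medications are recorded from screening (protocol 6.5), so the rule would also fit screening failures. Read with SAP 7.3 it allows for such patients, but no more than that.
- A reader might infer that visit-by-visit summaries are materially contaminated. SAP 9.1 defines baseline relative to the first dose, so an undosed patient has no defined baseline and no change from it. Such a patient could contribute later values only by attending a further visit, for example the discontinuation visit that protocol 7.4 asks sites to attempt.

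What survives is the definitional mismatch. It exists whatever the count, and the plan does not require the count to be reported.

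**Conclusion.** The point holds in conditional form. As written, the Safety Population admits patients who cannot have a TEAE, and SAP 9.5 makes it the set for the TEAE and drug-related TEAE tables. If any of the 47 went undosed, those percentages would be too low; if none did, the Safety Population and ITT coincide and nothing changes.

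The relative understatement is between 0% and 4.3%. This rests on three things: the counts in SAP 4.1, the assumption that all 45 completers took at least one dose, and the inference from SAP 9.5 that the TEAE denominators are all included patients. This is not a protocol–SAP discrepancy, since the two definitions match. It does not affect the efficacy conclusions. It is a low-priority correction, worth making because the error can go in only one direction and costs almost nothing to remove.

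**What to change.** In SAP 6.3 and 9.5.2, with an entry under the SAP's own heading for changes from the study protocol:

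- Use included patients who received at least one dose (the existing ITT/FAS set) as the denominator for the TEAE tables, including the serious and drug-related versions, and for on-treatment safety summaries.
- Keep all included patients as the denominator for the pre-treatment AE tables.
- Report the number of patients included but never dosed, and list any events they had.
- State the denominator in 9.5.2, so that it need not be inferred from 9.5.

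The cost is a few lines of SAP text and one extra denominator in the safety outputs. The AE percentages may become slightly less favourable, within the bounds above. If the number never dosed is zero, one sentence saying so settles the matter.

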### **6.4 OTHER ANALYSIS SET**

#### **MODIFIED INTENTION-TO-TREAT POPULATION (ITT)**

All included patients who received at least one dose of the study medication and performed at least Visit 2 and Visit 3 laboratory assessments under the same LT4 dose with a valid TSH value.

### **6.5 TREATMENT MISALLOCATIONS**

Not applicable.

### **6.6 PROTOCOL DEVIATIONS**

Any protocol violation or deviation (i.e., wrong inclusion, poor compliance, forbidden concomitant medications etc.) will be discussed by case before statistical analysis with the clinical team and described in the statistical report.

Violations will be classified as major violation or minor violation according to the impact on subject safety, the effect on completeness, accuracy and reliability of the data collected for the study, and the influence on the efficacy assessments. Protocol deviations related to COVID-19 will also be identified.

## 7 VARIABLES OF INTEREST

### 7.1 EFFICACY VARIABLES

#### 7.1.1 Primary efficacy variables

The primary efficacy variable is the serum levels of TSH.

Serum levels of TSH will be measured at screening visit(s), at baseline, halfway through the treatment period and at the final visit.

The serum levels of TSH recorded after changes in LT4 dose will not be considered for the analysis.

#### 7.1.2 Secondary efficacy variables

The secondary efficacy variables are the serum levels of FT4, TT4, FT3, TT3, CPK, SHBG, ferritin, ACE level, and lipid panel; and the LT4 dose adjustment.

Serum levels of FT4, FT3 and TT3 will be measured at screening visit(s), at baseline, halfway through the treatment period and at the final visit. In addition, serum levels of TT4, CPK, SHBG, ferritin, ACE level, and lipid panel (TC, HDL-C, LDL-C, VLDL-C, TG) will be measured at baseline and at the end of the 12-week treatment period (Final visit).

The change in serum levels of TSH, FT4, FT3, TT3 at Visit 3 vs baseline will also be analysed as secondary efficacy endpoint.

The serum levels of TSH, FT4, TT4, FT3, TT3, CPK, SHBG, ferritin, ACE level, and lipid panel recorded after changes in LT4 dose will not be considered for the analysis.

LT4 dose adjustment will be evaluated both in terms of number of patients requiring changes in daily dose during the treatment period and as mean change in daily LT4 dose at the end of the treatment period versus baseline.

